1.2.6 Rationale

Localized clear cell renal carcinoma in VHL patients requires surgical therapy, which often needs to be repeated multiple times. The surgical therapy is not curative, but is recommended in order to decrease the likelihood of metastasis. Once metastasis has occurred, clear cell renal cancer is incurable in the majority of VHL patients with currently available therapies.

Insight into the molecular pathways believed to mediate the VHL phenotype has provided the impetus for the development of rational targeted therapeutic strategies directed against this condition. Inactivation of the *VHL* gene, the underlying molecular defect in VHL, results in decreased ubiquitin-dependent degradation of hypoxia-inducible factors (HIFs), which in turn leads to overexpression of VEGF as well as other genes such as transforming growth factor- β (TGF- β), platelet derived growth factor (PDGF) and GLUT-1. Overexpression of VEGF is responsible for enhanced tumor angiogenesis and leads to the highly vascular renal tumors seen in VHL patients. ZD6474 inhibits angiogenesis by inactivation of the tyrosine kinase activity of the VEGF receptor KDR/VEGFR2. In addition, ZD6474 may exert direct antitumor activity via its inhibition of EGF- R, one of the ligands for which is TGF- β . ZD6474 has shown activity in several preclinical tumor models and has demonstrated an acceptable toxicity profile in phase I and phase II studies. ZD6474 thus provides an exciting opportunity for exploring a targeted approach in a hereditary syndrome with a well characterized molecular defect and no available curative options.

2 ELIGIBILITY ASSESSMENT AND ENROLLMENT

2.1 ELIGIBILITY CRITERIA

2.1.1 Inclusion Criteria

- Patients must satisfy all the following criteria to be eligible for study enrolment

- Clinical diagnosis of von Hippel Lindau disease ([Appendix E](#))
- The presence of at least one measurable (as defined by RECIST) renal tumor (RCC). Patients with tumors localized to the kidney as well as those with metastatic RCC are eligible.
- Age \geq 18 years.
- Life expectancy $>$ 3 months
- Performance status ECOG 0-2
- Patients must have normal organ and marrow function as defined below: WBC count \geq 3,000/uL, absolute neutrophil count \geq 1,500/ \square , platelet count \geq 100,000/ \square , serum creatinine \leq 1.5 times upper limit of reference range or measured 24 hr. creatinine clearance \geq 50 ml/min, AST and ALT $<$ 2.5 x upper limit of reference range, total bilirubin $<$ 1.5x upper limit of reference range ($<$ 3 x upper limit of reference range in patients with Gilbert's disease), alkaline phosphatase \leq 2.5 x upper limit of reference range (or \leq 5 x upper limit of reference range if considered to be related to liver metastases by the PI)
- No history of serious intercurrent medical illness
- At least four weeks from completion of any other surgical or investigational therapy for von Hippel Lindau and at least 4 weeks from any major surgical procedure. In addition, patients who have undergone recent major surgery should have well healed surgical incisions.
- All men and women of childbearing potential must use effective contraception
- Negative pregnancy test in female patients of childbearing potential within 7 days prior to enrolment on study
- Ability to understand and the willingness to sign a written informed consent document.

2.1.2 Exclusion Criteria

- Prior or concomitant non-von Hippel Lindau associated malignancy with the exception of adequately treated basal or squamous cell carcinoma of the skin, cervical carcinoma in situ or any other malignancy from which the patient has remained disease free for more than five years
- Known brain metastases (unless adequately resected or irradiated with no evidence of recurrence for at least 6 months)
- Patients who have had chemotherapy or radiotherapy within 4 weeks prior to entering the study or those who have not recovered from adverse events (to \leq grade 1 CTCAE v3.0) due to agents administered more than 4 weeks earlier.
- Patients may not be receiving any other investigational agents or have received treatment with a non-approved or investigational drug within 4 weeks prior to Day 1 of study treatment except those used for imaging studies. Use of 5HT-3 antagonists because of the potential effect on QTc interval
- Any concurrent medication that may cause QTc prolongation or induce Torsades de Pointes ([Appendix C](#)). Drugs listed in [Appendix C](#), Table 2, that in the investigator's opinion cannot be discontinued, are allowed however, must be monitored closely.
- Concomitant medications that are potent inducers of CYP3A4 function, such as rifampin, rifabutin, phenytoin, carbamazepine, barbiturates such as phenobarbital, or

St. John's Wort (See [Appendix D](#)).

- Clinically significant cardiac event (including symptomatic heart failure, myocardial infarction or angina) within 3 months of entry or presence of any cardiac disease that in the opinion of the Principal Investigator increases the risk of ventricular arrhythmia
- History of clinically significant arrhythmia [including multifocal premature ventricular contraction (PVC), bigeminy, trigeminy, ventricular tachycardia] that is symptomatic or requires treatment (CTCAE grade 3) or asymptomatic sustained ventricular tachycardia
- Uncontrolled atrial fibrillation. Atrial fibrillation controlled on medication is not excluded.
- Presence of Left bundle branch block
- Previous history of QTc prolongation while taking other medications that required discontinuation of that medication.
- Congenital long QT syndrome or first degree relative with unexplained sudden death under the age of 40 years
- QTc with Bazett's correction that is unmeasurable, or ≥ 480 msec on screening ECG. If a patient has QTc ≥ 480 msec on screening ECG, the screen ECG may be repeated twice (at least 24 hours apart). The average QTc from the three screening ECGs must be < 480 msec in order for the patient to be eligible for the study). Patients who are receiving a drug that has a risk of QTc prolongation (see [Appendix C](#), Group/Table 2) are excluded if QTc is ≥ 460 msec.
- Potassium concentration less than 4.0 mEq/L, calcium (ionized calcium or adjusted for albumin), or magnesium concentrations outside normal limits despite optimal supplementation/correction
- Left ventricular ejection fraction less than 45% measured by multiple gated acquisition scan (MUGA) or echocardiogram (ECHO)
- Hypertension not controlled by medical therapy (systolic blood pressure greater than 150 mmHg or diastolic blood pressure greater than 100 mmHg).
- Uncontrolled intercurrent illness including, but not limited to, ongoing or active infection, symptomatic congestive heart failure, unstable angina pectoris, cardiac arrhythmia, or psychiatric illness/social situations that would limit compliance with study requirements.
- Patient known to be HIV positive and requiring antiretroviral therapy
- Currently active diarrhea that may affect the ability of the patient to absorb ZD6474 or tolerate further diarrhea.
- Patients on therapeutic anticoagulation
- Patients with known bleeding disorders
- Pregnant women are excluded from this study because ZD6474 is an anti-angiogenic agent with the potential for teratogenic or abortifacient effects. Because there is an unknown but potential risk for adverse events in nursing infants secondary to treatment of the mother with ZD6474, breastfeeding should be discontinued if the mother is treated with ZD6474
- Any known hypersensitivity to ZD 6474 or other excipients of ZD6474

2.1.3 Restrictions

- Patients who are blood donors should not donate blood during the trial and for 3 months following their last dose of trial treatment.
- Due to the experimental nature of ZD6474, female patients must be one year post-menopausal, surgically sterile, or using an acceptable method of contraception during and continued after the last dose of study med (oral contraceptives, barrier methods, approved contraceptive implant, long-term injectable contraception, intrauterine device or tubal ligation.) Male patients must be surgically sterile or using an acceptable method of contraception during their participation in this study. Contraceptive use will continue for at least two months, five half-lives, after the last dose of study medication.
- Both men and women and members of all races and ethnic groups are eligible for this trial.

2.2 RESEARCH ELIGIBILITY EVALUATION

2.2.1 History and Physical

Complete history and physical examination and assessment of performance status will be obtained at the first clinic visit (screening visit) followed by interim assessments at each visit. The H&P and performance status need only be recorded upon the initial assessment and where pertinent changes (improvement or deterioration of previously abnormal findings, new findings or a change in performance status) are noted. Patients will be asked to keep a diary of their side effects, time of occurrence, and medications or interventions for relief. This will be reviewed with the team at each visit.

2.2.2 The following must be performed within 4 weeks of enrollment on study

- Imaging studies: PA and lateral chest X-ray, CT of the chest, abdomen and pelvis (or MRI scans when indicated)
- MRI of brain to include: pre-contrast T-1 and T-2 weighted images in the axial plane and post-contrast (Gadolinium) T-1 weighted images in the axial, sagittal or coronal planes (1 hour scan time). CT imaging with and without contrast may be performed if MRI cannot be performed.
- ECHO
- 12 lead EKG

2.2.3 The following must be performed within 7 days of enrollment on study

History and physical - Limited interim evaluation focusing on significant changes or deviations from initial H&P

CBC with differential, Chem 20 panel, urinalysis

Urine or serum pregnancy test in women of childbearing potential.

2.3 REGISTRATION PROCEDURES

Authorized staff must register an eligible candidate with NCI Central Registration Office (CRO) within 24 hours of signing consent. A registration Eligibility Checklist from the web site

(<http://home.ccr.cancer.gov/intra/eligibility/welcome.htm>)

must be completed and faxed to [contact]. After confirmation of eligibility at Central Registration Office, CRO staff will call the pharmacy to advise them of the acceptance of the patient on the protocol prior to the release of any investigational agents. Verification of Registration will be forwarded electronically via e-mail. *Please note, it is very important for all registrars to acquire encrypted e-mail from NIH Help Desk, since the verification of registration includes patient's information.* A recorder is available during non-working hours. The Central Registration Office will be notified when a patient is withdrawn from the study.

3 STUDY IMPLEMENTATION

3.1 STUDY DESIGN

This is a phase II study utilizing a fixed dose of ZD6474 (300mg/day PO). The study will recruit patients with von Hippel Lindau disease who have at least one measurable renal tumor (either localized to the kidneys and/or metastatic). Based on phase I evaluation, 300mg/day was identified as a well tolerated dose and appears to result in serum concentrations of the drug compatible with inhibition of target receptor tyrosine kinases. Treatment cycles will consist of 28 days and the drug will be administered daily on days 1-28. There will be no break between 2 consecutive cycles (i.e, drug administration will be continuous). Patients will undergo clinical and laboratory evaluation in the Urologic Oncology Branch clinic prior to the start of each cycle. Patients will be evaluated radiologically for evidence of response or progression approximately twelve weeks after initiation of therapy and every twelve weeks thereafter while on study. Patients with evidence of stable disease or disease response in renal tumors (CR or PR) will continue to receive therapy in the absence of serious toxicity. Patients who demonstrate disease progression at any time will be taken off study. Patients who continue to demonstrate at least one tumor >3cm following 12 weeks or more of therapy may be taken off study regardless of response status, if, in the opinion of the PI, this lesion(s) poses a significant risk of metastasis in the absence of surgical intervention or could otherwise compromise patient care. These patients will be evaluable for the primary end-point (disease response).

Non-renal VHL associated lesions are usually followed until they reach a certain size or become symptomatic, at which point surgical resection or other treatments (such as laser photocoagulation of retinal angiomas) of these lesions is pursued. It is also conceivable, although unlikely, that patients with pheochromocytomas or pancreatic neuroendocrine tumors may develop metastatic disease that may necessitate chemotherapy. Patients with progression of non-renal lesions requiring systemic antineoplastic therapy or surgical intervention will discontinue study drug even in the absence of renal progression or unacceptable toxicity. Vandetanib may be restarted in patients undergoing resection of non-renal VHL lesions once the surgical incisions have adequately healed, if in the opinion of the PI, this is likely to offer clinical benefit (e.g. patients demonstrating an ongoing response in their renal tumors while on vandetanib). Patients with progression of non-renal lesions not requiring intervention but demonstrating stable or responding renal lesions will continue ZD6474 at the discretion of the PI/Study Chair.

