3.10 POST-TREATMENT FOLLOW-UP

Patients with unresolved toxicities (to \leq CTCAE 3.0 grade 1) may be followed to enable monitoring and/or management of these toxicities. Patients may be followed-up by telephone or other means of communication periodically to determine disease status.

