5 DATA COLLECTION AND EVALUATION

5.1 DATA COLLECTION

Data will be prospectively collected and entered in a designated database (C3D). All radiographic images will be stored in the Dept. of Radiology, Clinical Center, NIH and will be reviewed by a medically responsible investigator and/or a clinical center radiologist.

For the purposes of this study, patients should be reevaluated for response every 12 weeks. In addition to a baseline scan, confirmatory scans should also be obtained 4 weeks following initial documentation of objective response.

The PI will be responsible for overseeing entry of data into an in-house password protected electronic system and ensuring data accuracy, consistency and timeliness. The principal investigator, associate investigators/research nurses and/or a contracted data manager will assist with the data management efforts. All data obtained during the conduct of the protocol will be kept in secure network drives or in approved alternative sites that comply with NIH security standards. Primary and final analyzed data will have identifiers so that research data can be attributed to an individual human subject participant.

End of study procedures: Data will be stored according to HHS, FDA regulations and NIH Intramural Records Retention Schedule as applicable.

Loss or destruction of data: Should we become aware that a major breach in our plan to protect subject confidentiality and trial data has occurred, the IRB will be notified.

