5.2.1.3 Target lesions

All measurable RCC lesions up to a maximum of five lesions per kidney and a total of ten lesions should be identified as **target lesions** and recorded and measured at baseline. Target lesions should be selected on the basis of their size (lesions with the longest diameter) and their suitability for accurate repeated measurements (either by imaging techniques or clinically). A sum of the longest diameter (LD) for all target lesions will be calculated and reported as the baseline sum LD. The baseline sum LD will be used as reference by which to characterize the objective tumor response.

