5.2.4 Confirmatory Measurement/Duration of Response

5.2.4.1 Confirmation

To be assigned a status of PR or CR, changes in tumor measurements must be confirmed by repeat assessments that should be performed ≥ 4 weeks after the criteria for response are first met. In the case of SD, follow-up measurements must have met the SD criteria at least once after study entry at a minimum interval of 8 weeks

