6 STATISTICAL SECTION

This is a phase II study to establish whether treatment of ZD6474 in patients with von Hippel Lindau disease and renal tumors results in an adequate fraction of clinical responses (partial response plus complete response) to warrant further development. The study will be conducted with a Simon two-stage optimal design (Simon R. Controlled Clinical Trials 10:1-10;1989) which allows for an early look for futility. For the purposes of phase II evaluation, clinical response will be defined as either a partial or complete response occurring at any time after initiation of therapy. All responses must be confirmed ≥ 4 weeks after the initial response is documented. Twelve patients will be accrued into the first stage. If 1 or more of the 12 patients respond, accrual will proceed to the second stage of the design. Twenty-five additional patients will be accrued in the second stage for a total accrual of 37 patients. If 4 or more of 37 respond, ZD6474 will be considered worthy of further investigation in this population. If fewer than 4 patients of 37 respond, the agent will be considered to have insufficient activity for further investigation. If after the first 12 patients have been accrued to the study, no patient has had a confirmed response, further accrual will be temporarily suspended for up to a year or until at least one response is seen; if no responses are seen within one year of accrual of the twelfth patient, no further patients will be accrued and the study will not proceed to the second stage.

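### Does removing patients for a tumor over 3 cm lose responses for lack of a confirmatory scan, or leave PFS and TTP without a workable rule?

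*Combined protocol and SAP*

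**What the plan says.** Section 3.1 schedules radiological evaluation at about twelve weeks and "every twelve weeks thereafter while on study". Patients with stable or responding renal tumors continue by default. The exception is a patient with at least one tumor still above 3 cm after 12 weeks or more, who "may be taken off study regardless of response status, if, in the opinion of the PI, this lesion(s) poses a significant risk of metastasis" without surgery, or if care could otherwise be compromised. The same section says these patients remain evaluable for the primary endpoint.

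On confirmation, section 5.1 says that "confirmatory scans should also be obtained 4 weeks following initial documentation of objective response". Section 5.2.4.1 says that for PR or CR "changes in tumor measurements must be confirmed by repeat assessments that should be performed" at least 4 weeks after the criteria are first met. Section 5.2.3.3 makes the best response depend on confirmation as well as measurement. Section 6 requires every response to be confirmed and applies this at the first stage: "If after the first 12 patients have been accrued to the study, no patient has had a confirmed response", accrual is suspended for up to a year while a response is awaited.

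On what follows removal, section 3.10 says only that "Patients may be followed-up by telephone or other means of communication periodically to determine disease status", and the calendar in section 3.6 marks no RECIST assessment at withdrawal. Section 6.2 defines PFS by RECIST progression or death. It defines TTP by progression with deaths censored, and summarizes both with Kaplan-Meier curves.

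**The concern.** The removal rule starts at the same time as the first on-treatment scan, about week 12. A patient could meet PR at that scan, still have one tumor above 3 cm, and be taken off study the same day. Routine restaging then ends and later contact may be by telephone. If no further scan were done, a patient declared evaluable would have no route to a confirmed response and would count as a failure. The cut-offs are 1 of 12 and 4 of 37, so one lost response can change a decision, and the cost would be a higher chance of dropping an active drug.

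The second worry is PFS and TTP. Removal is neither progression nor death, and the plan does not say how it enters the curves. Patients are chosen for removal because the investigator sees metastatic risk, so censoring them may be informative. Section 3.9 also omits this reason from its list of off-study criteria.

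**Working it through.** **1. Can the situation arise?** Yes. Under section 5.2.1.3, "A sum of the longest diameter (LD) for all target lesions will be calculated and reported as the baseline sum LD", and PR is a fall of at least 30% in that sum. As an invented example, tumors of 3.5 + 2.0 + 2.0 + 2.0 = 9.5 cm shrink to 3.2 + 1.2 + 1.1 + 1.1 = 6.6 cm. The fall is (9.5 − 6.6)/9.5 = 30.5%, with one tumor still above 3 cm.

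**2. Does the plan provide the scan?** The limit to time on study in section 3.1 belongs to the 12-weekly restaging. The confirmatory scan in section 5.1 is triggered by the first documented response and carries no such limit.

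**3. Is there time for it?** Take the tightest case, a PR at week 12 with the drug stopped that day. Section 3.8 keeps major elective surgery at least 4 weeks from the last dose, so not before week 12 + 4 = week 16. The confirmatory scan is due from week 12 + 4 = week 16. The two meet even here. Section 7.2.2 reports that surgery often follows its recommendation by 3 to 4 months, so there is usually slack. Removal is also discretionary. At the first stage, the suspension of up to a year allows a confirmation to arrive.

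**4. How is a patient without the scan classified?** Sections 5.2.3.3, 5.2.4.1 and 6 agree: not a responder. Being evaluable puts the patient in the denominator. It does not waive confirmation.

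**5. The design's own figures.** Inputs from sections 6 and 6.1: 12 patients in stage 1, continue with at least 1 response; 25 more; success with at least 4 of 37; null rate 5%, target 20%. With response rate p,

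P(success) = Σ over x = 1 to 12 of P[Bin(12, p) = x] × P[Bin(25, p) ≥ max(0, 4 − x)].

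- p = 0.05: type I error 0.0935 (ceiling 0.10).
- p = 0.20: power 0.9024 (planned 0.90).
- Early stop at p = 0.05: 0.95^12 = 0.540 (stated 54%).

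**6. Effect of lost confirmations.** The documents give no loss rate, so q below is an assumption; replace p by p(1 − q).

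| q | power at 20% | stage-1 stop at 20% | type I error at 5% |
|---|---|---|---|
| 0 | 0.902 | 6.9% | 0.094 |
| 5% | 0.882 | 8.0% | 0.081 |
| 10% | 0.857 | 9.2% | 0.070 |
| 20% | 0.792 | 12.3% | 0.049 |

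The table treats 20% as the rate before confirmation is lost. Section 6 builds confirmation into the definition of response, so the 20% target is most naturally a confirmed rate and the planned power already applies to it. Relaxing confirmation would work the other way: if counting unconfirmed responses raised the null rate to 5.5% or 6% (assumed), type I error would be 0.121 or 0.151.

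**7. PFS and TTP.** A patient with neither event is censored at the last assessment under Kaplan-Meier estimation. Suppose k of 37 are removed at the first scan and 60% of the rest are later progression-free (both assumed). With removals censored the estimate is 60%. With removals as events it is (1 − k/37) × 60%:

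- k = 2: 56.8% (gap 3.2 points)
- k = 4: 53.5% (gap 6.5)
- k = 6: 50.3% (gap 9.7)

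The sampling margin is 1.96 × √(0.6 × 0.4/37) = 15.8 points.

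**The case for a change.** The best case for a change is that section 5.1 says what should happen in general and never mentions patients taken off study, while the calendar and section 3.10 suggest that imaging ends. Leaving this to case-by-case judgment in an open-label, single-arm trial is not ideal. Nor would a loss be trivial. At a 20% rate the expected number of responders is 37 × 0.20 = 7.4, so one lost per trial is 1/7.4 = 13.5% of them. Power would then lie between 0.857 (q = 10%) and 0.827 (q = 15%). At that rate, 20.6% of trials have exactly one response in the first 12.

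The silence is real and that arithmetic stands. But a loss needs four things together: PR first met at the removal scan, a tumor still above 3 cm, a decision to remove at once, and the section 5.1 scan not done. The last is a departure from the plan, not a result of following it. The 20.6% is the chance of standing at a boundary, not the chance of a wrong decision.

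On PFS and TTP, informative censoring is a fair point, and a bias is not excused by being smaller than the sampling error. But the missing censoring rule applies equally to toxicity and withdrawal, and counting a removal without progression as an event is itself debatable.

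**Conclusion.** No change is needed. For the primary endpoint, the plan followed as written calls for the confirmatory scan, leaves time for it, and states how a response without it is classified. Requiring confirmation is a fair trade: any loss lowers type I error below 0.0935 at some cost in power, and that cost cannot be sized from the documents. This rests on reading section 5.1 as applying to any patient with a first response, which its wording supports, and on the drug not having been stopped well before the scan.

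For PFS and TTP the gap is one that analysts fill sensibly. The events are defined, so removals are censored at the last assessment. The curves are secondary and descriptive, with no test or decision attached. The illustrated shift of 3.2 to 9.7 points depends on invented counts.

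The list in section 3.9 does not contradict section 3.1. Section 3.1 states the removal rule expressly, and the item in 3.9 on investigator judgment can cover it.

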 - Elevated liver function tests, generally CTC/CTCAE grade 1-2. Preliminary data suggests these are reversible, in some cases even while continuing therapy.
- Metabolic and nutritional
 - Anorexia, dehydration, hypokalaemia, hypomagnesaemia, hypercalcemia and hypophosphataemia
- Skin and appendages
 - Acneiform rash, pruritus, macular or maculopapular rash (generalised or localised), localised and generalised erythema, photosensitivity reaction, and sweating. On occasion, especially when given with chemotherapy, these have progressed to more serious conditions, including exfoliative dermatitis, skin desquamation, erythroderma, toxicoderma, toxic epidermal necrolysis, erythema multiforme and necrotizing fasciitis.
 - Wound healing complications
 - Hand-foot syndrome
- Respiratory
 - Interstitial lung disease, pulmonary effusion and pneumonia. A very small number of patients with lung cancer receiving vandetanib have developed shortness of breath and cough because of inflammation or scar tissue formation in the lungs, although this could be due to the underlying lung cancer.
- Renal
 - Proteinuria, haematuria and renal failure.
- Vascular
 - Arterial ischaemic events (including myocardial infarction, stroke, peripheral ischaemia), venous thromboembolism (including pulmonary embolism). A small number of patients receiving vandetanib have developed blood clots affecting the legs or lungs. This may have been due to the patient's cancer or other illness at the time; however, it is considered possible that vandetanib might increase the risk for developing blood clots.
 - Intracranial bleeding
- Psychiatric
 - Mood disorders (anxiety, depression, insomnia). It is possible that these events are not direct effects of vandetanib, but rather are secondary to symptoms of cancer or to other effects of vandetanib (rash, etc).
- Ophthalmologic
 - Corneal changes, including ulceration
- General
 - Asthenia, fever, weight loss, pain, and fatigue

In addition, a number of other side effects have been reported in clinical trials using ZD6474 alone, in combination with other chemotherapy agents or radiation. It is unclear whether these side effects are related to ZD6474, or are caused by other factors (such as chemotherapy or

radiation). These side effects include:

- Infections, including life-threatening bacterial infections
- Seizures and facial nerve palsies
- Syncope
- LV dysfunction
- Respiratory failure
- Esophageal fistula

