3.8 SURGICAL GUIDELINES

Major elective surgical procedures should not be scheduled during protocol treatment or within 4 weeks of the last dose of drug. Patients undergoing unexpected major surgical procedures should have ZD6474 withheld. Treatment may be resumed at a later date at the discretion of the PI, no earlier than 4 weeks post-operatively, with adequately healed incisions.

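### Sections 3.1 and 3.9 set no minimum interval before restart after a non-renal resection, section 3.8 sets 4 weeks after unexpected major surgery, and section 5.2.5.3 takes such patients off study with no restart

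*Combined protocol and SAP*

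**What the plan says.** Four sections of the combined protocol and SAP bear on a patient who has a non-renal VHL lesion removed.

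- **Section 3.1 (Study Design).** "Patients with progression of non-renal lesions requiring systemic antineoplastic therapy or surgical intervention will discontinue study drug", even if the renal tumors have not progressed. Then: "Vandetanib may be restarted in patients undergoing resection of non-renal VHL lesions once the surgical incisions have adequately healed", with the further condition "if in the opinion of the PI, this is likely to offer clinical benefit". The example given is a patient whose renal tumors are still responding. No minimum interval is stated.
- **Section 3.9 (Off Study Criteria/Off Treatment Criteria).** The restart sentence of 3.1 appears again, also without an interval.
- **Section 3.8 (Surgical Guidelines).** For elective work: "Major elective surgical procedures should not be scheduled during protocol treatment or within 4 weeks of the last dose of drug". For other work: "Patients undergoing unexpected major surgical procedures should have ZD6474 withheld". The next sentence is the restart rule: "Treatment may be resumed at a later date at the discretion of the PI, no earlier than 4 weeks post-operatively, with adequately healed incisions".
- **Section 5.2.5.3 (non-renal tumors).** Patients whose progressing non-renal lesions need medical or surgical intervention leave the study as having progressive disease. Resumption is not mentioned.

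None of these sections refers to another on this point, and none says which prevails.

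**The concern.** Resection is the usual management of non-renal VHL lesions (sections 1.2.4 and 3.1), so a patient on study may well need one. The adverse event list in section 1.2.5 includes "Wound healing complications" and intracranial bleeding. Section 7.2.2 names bleeding from cerebellar or spinal hemangioblastomas as a possible risk in this population. The timing of a restart after surgery is therefore a safety rule, and it should give one answer.

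Three things are at stake. First, a site following 3.1 or 3.9 could restart the drug at a time when 3.8 does not allow it. Second, the same restart would comply with one section and deviate from another, while section 8.2.1 requires all protocol deviations to be reported. Third, section 5.2.5.3 ends study participation for patients whom 3.1 and 3.9 expect may resume. Whether such a patient is handled as a progressor who has left the study or as a continuing patient bears on how time to progression and progression-free survival (section 6.2) are recorded.

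**Working it through.** No arithmetic applies. The check sets the rules side by side, one situation at a time.

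**Step 1: the conditions for restart.**
- 3.1 and 3.9: healed incisions, and the investigator expects benefit.
- 3.8: at least 4 weeks since the operation, healed incisions, and the investigator's discretion.
- 5.2.5.3: no restart route.

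Investigator judgment appears in both 3.1/3.9 and 3.8. The timing difference is the 4-week minimum.

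**Step 2: can healed incisions be taken to mean 4 weeks?** No. Section 3.8 lists the interval and the healing as two conditions. The inclusion criteria in section 2.1.1 do the same for surgery before entry: 4 weeks from major surgery and, as an addition, well healed incisions. The document treats time and healing as separate tests, so healing alone in 3.1 and 3.9 cannot be assumed to carry the interval.

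**Step 3: the scope of the 3.8 minimum.** It follows directly on a sentence about unexpected major procedures. Read literally, it covers those only. A planned major resection is not unexpected, and a minor procedure is not major.

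**Step 4: apply the rules.** The last column applies where the operation is for non-renal progression.

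| Operation and state | 3.1 / 3.9 | 3.8 | 5.2.5.3 |
|---|---|---|---|
| Unexpected major, healed, before week 4 | Restart permitted | Restart not permitted | Off study |
| Unexpected major, healed, week 4 or later | Permitted | Permitted | Off study |
| Unexpected major, not healed | Not permitted | Not permitted | Off study |
| Planned major, healed, before week 4 | Permitted | Not stated whether the minimum applies | Off study |
| Minor, healed | Permitted | Outside its scope | Off study |

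**Result.** The first row is a direct conflict on timing. The fourth row is a gap: read literally, a planned major resection has no minimum interval while the same operation done unexpectedly has 4 weeks, and no reason is given. In every row where 3.1 and 3.9 permit a restart, 5.2.5.3 has already removed the patient if the operation was for progression.

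**The case against.** The strongest reply is that the rules can be followed together. Sections 3.1 and 3.9 give permission, 3.8 sets a floor, and a site that waits 4 weeks breaches neither. That is correct, and it limits the timing conflict to unexpected major resections that heal before week 4. It does not remove the conflict, because a reader of 3.1 or 3.9 has an explicit permission and no pointer to the floor. Nor does waiting resolve the conflict with 5.2.5.3, where the question is whether the patient remains on study.

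A second reply is that the sections have different scopes: 3.8 concerns major surgery, with its restart sentence placed after unexpected procedures, while 3.1 and 3.9 concern any non-renal resection. This stands. The conflict therefore must not be extended to every non-renal resection. For planned major operations the fault is an unstated scope.

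Two stronger readings are tempting, and the documents support neither.

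- A reader might infer a contradiction before surgery as well, since 3.8 keeps major elective operations 4 weeks from the last dose and 3.1 gives no gap. But 3.1 only stops the drug. A site can stop it under 3.1 and schedule the operation under 3.8. This is silence, not contradiction.
- A reader might use the terminal half-life of about 4 to 5 days in section 1.2.5 to express the difference as residual drug. That calculation needs a shorter interval to compare with 4 weeks, and 3.1 and 3.9 supply none. It also describes washout after the last dose, which is the pre-operative side, where there is no conflict. Exposure after a restart is a different quantity.

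**Conclusion.** The point holds in a limited form. For an unexpected major resection of a non-renal lesion whose incisions heal before week 4, sections 3.1 and 3.9 and section 3.8 give opposite answers on restart. For planned major resections the documents do not say whether the 4-week minimum applies. Section 5.2.5.3 conflicts with 3.1 and 3.9 on whether a patient operated on for non-renal progression may resume at all.

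The conclusion rests on two readings: that healed incisions do not imply 4 weeks, which sections 2.1.1 and 3.8 support, and that the 3.8 restart sentence is tied to the sentence before it. If that sentence were meant for all major surgery, the direct conflict would widen to planned major resections.

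No numerical size can be given. The documents state neither the expected number of non-renal operations nor the usual time to healing. No effect on the primary response endpoint, the two-stage rule or the 37 patients is claimed. The matter is worth correcting because it concerns a safety rule and the correction is cheap.

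**What to change.** Reconcile sections 3.1, 3.8, 3.9 and 5.2.5.3 in one amendment.

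1. State in one place, most naturally 3.8, which restart condition governs planned and unplanned major resections of non-renal lesions. Say explicitly whether the existing minimum interval covers both.
2. State whether patients operated on for non-renal progression leave the study or stop treatment with the possibility of resuming, and align 5.2.5.3 with 3.1 and 3.9 accordingly.
3. Replace the separate restart wording in 3.1 and 3.9 with a reference to that place, and add the same reference in 5.2.5.3.

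Which timing applies, and whether resumption is allowed, is for the investigators to decide. The cost is amendment wording. No additional patients or assessments are needed, and the sample size does not change.
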